### **Sample Size:**

This trial will randomize subjects 1:1 to Vapotherm:NIPPV. A total sample size of 64 subjects (~32 per arm) randomized with endpoint data, and a one-sided alpha of 0.025 will provide at least 80% power to demonstrate non-inferiority. This sample size assumes a difference of 0.9 between treatment and control with standard deviation of 2.4 and 2.9 for treatment and control, respectively, and a non-inferiority margin of 1.0.

Allowing for up to 20% attrition, approximately 80 subjects (40 per arm) will be enrolled in order to achieve 64 subjects with an endpoint.

From Doshi et al, comparable moderate-to-severe hypercapnic respiratory distress patient data was analyzed, which informed this sample size calculation's assumed difference and standard deviations in treatment (HVNI) and control (NIPPV) for the modified Borg score.

Change in modified Borg over 4 hours	Mean	Standard Deviation
NIPPV arm (Control)	-3.208	2.431
HVNI arm (Treatment)	-4.143	2.931

The minimal clinically important difference (MCID) for modified Borg was informed from literature, as a difference value of 1.0.

**NOTE:** As this is an Emergency Department or inpatient acute care study, and treatment is often immediate due to need for maintaining patient safety, there is an expected patient dropout (i.e. incomplete or unusable subject number) of randomized & enrolled patients into this study. After presenting to the ED or inpatient acute care setting, should the patients be transferred to another area of the hospital, the study procedures will continue until complete.

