**Vapotherm, Inc**  
**Hypercapnia Stabilization RCT NIPPV v HVNI**  
**Confidential**

## II. Overall Study Objective

The **overall objective** of this randomized study is to evaluate the efficacy of HVNI, in comparison to NIPPV, to clinically stabilize and provide respiratory therapy to patients who have COPD with moderate-to-severe hypercapnic respiratory distress upon presentation.

The **hypothesis**: HVNI is comparable to NIPPV in the stabilization and relief of moderate-to-severe hypercapnic respiratory distress upon presentation, by relieving the patient's dyspnea (breathlessness) within 4 hours to a comparable degree to NIPPV.

$$H_0: \mu_T \leq \mu_C - 1$$

$$H_a: \mu_T > \mu_C - 1,$$

where  $\mu_T$  and  $\mu_C$  are the improvement in modified BORG at 4 hours for treatment (Vapotherm) and control (NIPPV), respectively, and the non-inferiority margin is 1.

To test this hypothesis, the study will be conducted with the following specific aims:

**Aim #1: Primary Outcome.** The primary endpoint is to evaluate the patient's relief of dyspnea, as measured by the modified Borg, rated perceived dyspnea [RPD 0-10], during the 4-hour post-therapy initiation interval. These measurements will be compiled over the time course of the study – baseline, 30min, 1h, and 4h.

**Aim #2: Secondary Outcomes.** The secondary endpoints evaluate treatment failure (need for intubation), indices of Work of Breathing (patient vitals [HR, RR, SpO2]), patient's clinical stability during hypercapnic respiratory distress, as measured by an index of patient communication capability [Patient Stability Index: 0-10], venous blood gases (pH, PCO2, PO2, bicarbonate, base excess), basic metabolic panel\* (lactate, Na+, K+, Cl, glucose), and patient disposition (length of stay [LOS]). These measurements will be compiled over the time course of the study – baseline\*, 30min, 1h, and 4h. The Patient Stability Index is described in the protocol.

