## VIII. Statistical Analysis

The data analysis will be “per protocol,” and per the “intention-to-treat” model. Baseline patient demographics and characteristics will be summarized, compared, and appropriate statistical testing will be performed for the continuous and categorical variables. Primary outcomes will be analyzed for statistical significance to test the null hypothesis. Assuming a non-normal data distribution for this randomized study design, the non-parametric Wilcoxon Signed Rank Sum test will be performed with significance interval of 0.05 on all applicable variables. Parametric analytical analogues (e.g. t-test) will be used if the measurements present a normal distribution. Otherwise, for the categorical variables, the Fisher’s Exact test will be performed and shown by category. Data for patient parameters will be compared across treatment arms and time-period using Repeated Measures analysis ANOVAs to assess dependence on treatment and interactions with time. Data will be compared and graphed accordingly for a visual comparison with accompanied statistical notations. Significance will be accepted where  $p < 0.05$ . Analyses will be performed using SAS version 9.2 or higher or comparable statistical software.

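### The 80% power holds only for a margin-based comparison of means with HVNI truly 0.9 Borg points better, and Section VIII does not specify that test

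*Combined protocol and SAP*

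**What the plan says.** Section V (Sample Size) plans for "A total sample size of 64 subjects (~32 per arm) randomized with endpoint data", with "a one-sided alpha of 0.025" and a non-inferiority margin of 1.0, and says that this "will provide at least 80% power to demonstrate non-inferiority". The inputs are disclosed: "This sample size assumes a difference of 0.9 between treatment and control with standard deviation of 2.4 and 2.9 for treatment and control, respectively". That sentence gives no direction. The table below it does: the mean change in modified Borg over 4 hours is -3.208 (SD 2.431) for NIPPV and -4.143 (SD 2.931) for HVNI. Section V says these are prior-trial data "which informed this sample size calculation's assumed difference and standard deviations in treatment (HVNI) and control (NIPPV) for the modified Borg score".

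Section II states the hypothesis in words, that "HVNI is comparable to NIPPV in the stabilization and relief of moderate-to-severe hypercapnic respiratory distress upon presentation". It then states it formally: the null is that mean improvement on HVNI is at least 1 point less than on NIPPV, and the alternative is that it is not.

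Section VIII says the primary outcome will be tested against the null hypothesis. It then continues "Assuming a non-normal data distribution for this randomized study design" and makes a Wilcoxon test at 0.05 the default for all applicable variables, with a t-test if the data are normal. The margin, the one-sided 0.025 and a confidence limit do not appear in Section VIII.

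**The concern.** There are two linked difficulties.

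First, the power figure stands beside a hypothesis of comparability but is calculated at an HVNI advantage of 0.9, close to the 1.0 that Section V takes as the minimal clinically important difference. No power is given for any smaller advantage. A reader cannot tell from the sentence how quickly the chance of success falls.

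Second, the analysis section does not carry the design through. Sections II and V are about a difference in means set against a margin of 1. Section VIII names a test that compares distributions, mentions no margin, and has a label that mixes the paired signed-rank test with the two-sample rank-sum test. Run as written, it asks whether the arms differ. A non-significant answer to that question does not show non-inferiority.

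The trial's main conclusion is at stake: the test that decides it is not fixed in advance, and its chance of success is shown only at a favourable assumption.

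**Working it through.** **Inputs.** From Section V: 32 per arm with endpoint data, SDs 2.4 and 2.9, margin 1.0, one-sided alpha 0.025, assumed difference 0.9. Direction from the table: 4.143 - 3.208 = 0.935 points more improvement on HVNI.

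**Standard error.** SE = sqrt((2.4² + 2.9²)/32) = sqrt(14.17/32) = 0.665.

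**The plan's own figure.** The distance from the margin is 1.0 + 0.9 = 1.9, so the noncentrality is 1.9/0.665 = 2.86. Noncentral-t power with Welch degrees of freedom (59.9) is 80.2%; the pooled t-test gives 80.3% and the normal approximation 81.5%. The stated figure reproduces. Had the 0.9 favoured NIPPV, the distance would be 0.1 and power 3.5%, so the calculation must assume an HVNI advantage.

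**Same design, other true differences (Welch t):**

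| True HVNI advantage | Distance / SE | Power |
|---|---|---|
| +0.9 | 2.86 | 80.2% |
| +0.5 | 2.25 | 60% |
| +0.25 | 1.88 | 46% |
| 0 | 1.50 | 31.5% |

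For scale only, 80% power at a true difference of 0 would take 113 per arm by t-test.

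**What must be observed.** The two-sided 95% CI half-width is 2.00 × 0.665 = 1.33, wider than the margin. The lower limit exceeds -1 only if the observed difference exceeds -1 + 1.33 = +0.33. At the planned SDs, identical observed means would fail.

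**SD labels.** The text gives 2.4 to treatment and 2.9 to control; the table gives 2.431 to control and 2.931 to treatment. At 1:1 the SE uses only the sum of the squares, so swapping the labels changes nothing. Unrounded table SDs give 79.3% at 0.9 and 80.8% at 0.935 (pooled t), which is rounding.

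**The test in Section VIII.** Without the margin, the distance at a true advantage of 0.9 is 0.9 instead of 1.9. A t-test then has 26.5% power. A two-sample rank-sum test without the margin has roughly one chance in four, by simulation with normal data assumed. Neither addresses the Section II null.

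If the rank-sum test is instead shifted by the margin at one-sided 0.025, its power at +0.9 depends on the shape of the data. Simulations with shapes assumed for this check (32 per arm, SDs 2.4 and 2.9) gave:

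| Assumed shape | Rank-sum power at +0.9 |
|---|---|
| Normal | 78% |
| Uniform | 74% |
| t with 5 df | 87% |
| Skewed gamma | 87% (test size inflated to 3.8%) |
| Laplace | 90% |

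The documents do not give the shape, so no one of these is the plan's power.

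**The case against.** The strongest reply is that nothing has been miscalculated or hidden. The 80% reproduces from the listed inputs, the 0.9 is stated, and its direction can be read from the table in the same section. A non-inferiority trial may be powered at a non-zero expected difference, and this one cites comparable patients in an earlier randomized trial. All of that stands. Whether 0.9 is optimistic cannot be judged from these documents.

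A reader might infer that power is about 31% under the trial's own hypothesis, taking comparable to mean equal. The documents do not support that. Section II defines the alternative as HVNI being less than 1 point worse, and true differences of 0 and of +0.9 both lie inside it. The 31% is power at one point of that alternative, which is a good reason to show it but does not make the stated figure wrong.

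A reader might also infer that the plan really has 78% power because Wilcoxon is the default, or that 80% needs a t-test. That does not follow either. The 78% assumes normal data, and for normal data Section VIII switches to the t-test; following that rule in simulation gave about 79 to 81%. For non-normal data, rank-sum power may be higher or lower.

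Finally, Section VIII does say the primary outcome is tested against the null hypothesis, so a shift by the margin may be intended, and a two-sided 0.05 would match a one-sided 0.025. But neither is written. If 0.05 were applied one-sided, power at +0.9 would be 88%, at twice the planned error rate. The objection therefore answers any charge of arithmetic error but leaves the gap in Section VIII open.

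**Conclusion.** The concern holds as a mismatch between the design and the analysis, together with a power statement that shows only its favourable case. It is not an arithmetic error. At least 80% is correct for a margin-based comparison of means at one-sided 0.025 with HVNI truly 0.9 points better. With the same 32 per arm and SDs, power is about 60% at +0.5 and 31% at 0, and success needs an observed HVNI advantage of about 0.33. These figures assume the planned SDs and full endpoint data on 64 subjects.

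The part that is wrong as written is Section VIII. Its default test omits the margin, the one-sided level and the mean difference, so it cannot test the Section II null and is not the test that was powered. No Wilcoxon power figure should be attached to the plan. The SD labels are a clerical contradiction with no effect on power at 1:1.

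**What to change.** In Section VIII, name one primary test: the between-arm difference in mean Borg improvement at 4 hours, HVNI minus NIPPV, with non-inferiority declared if the lower limit of the two-sided 95% CI exceeds -1 (one-sided 0.025). Keep a two-sample rank-sum test, shifted by the margin, as a sensitivity analysis, and correct its name.

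In Section V, say that the 80% assumes HVNI is 0.9 points better, and give power at +0.5 (about 60%) and at 0 (about 31%) beside it. Reconcile the SD labels in the sentence with those in the table.

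The cost is a small change to the analysis text, which does alter the named primary test, and a less favourable power statement. No extra patients or procedures are needed.

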# Vapotherm, Inc

## Hypercapnia Stabilization RCT NIPPV v HVNI

Confidential

[figure not shown]
### VI. Study Procedures

This head-to-head non-inferiority randomized control trial is non-blinded by necessity, as the devices are different in size, apparatus, and appearance, when viewed by both patients and clinicians. Patients may prefer HVNI over NIPPV or NIPPV over HVNI; however, this will not play a role in patient randomization. The study is a 1:1 randomized control design trial that will measure & compare the physiologic effect of the tested devices, specifically the effect on relieving patient dyspnea, and the stabilization and improvement of patient pH and PCO2 (venous blood gas). In addition, patient physiologic outcomes (e.g. HR, RR, BP, SpO2), patient disposition (LOS), patient venous blood gases (pH, PCO2, PO2, bicarbonate, base excess,) and patient & clinician assessment scores will be assessed and documented. Figure 1 illustrates a flowchart of overall study procedures. Except for the randomized study arm (HVNI or NIPPV device), the study procedures are identical.

#### Screening, Enrollment, & Management

Upon screening and fitting subject selection criteria, known at time of presentation to the ED or Acute Care unit for treatment, subjects may or may not be able to be asked to be randomized and enrolled into this study. In ED or Acute Care settings, there is a need to treat immediately to maintain patient safety. As such, consent in this study will take place through verbal consent prior to participation/randomization followed by written consent (when respiratory symptoms are manageable), or written consent prior to participation/randomization. Patients will be reassured that their medical care will not be impacted in any way and their medical providers will not change. All patients randomized, but not included in the final study population, will be accounted for in a CONSORT diagram, noting the dropout criteria (i.e. refused consent, met exclusion criteria, incomplete dataset, etc.). All study procedures will be explained to the subject.

Subjects will be managed by routine care while study data is captured as shown in the timeline below (Table 1). All decision making for patient participation will be made per standard practice/care at the trial site, relying on the judgment of qualified medical professionals on staff.

**Figure 1. Framework of the clinical study procedures discussed within this protocol for the two study arms: HVNI and NIPPV.**

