**Vapotherm, Inc**  
**Hypercapnia Stabilization RCT NIPPV v HVNI**  
**Confidential**

This study will be conducted in an Emergency Department or Inpatient Critical Care setting, if applicable, where patient care and testing can be performed with appropriate supervision and staff training to maintain patient safety. In this acute-care setting study, participants may or may not decide to enroll after being consented. Patients may be excluded after randomization, as this study takes place in the ED or inpatient critical care unit and patients may need to be randomized and treated immediately to maintain patient safety. All respiratory interventions will be tracked during the study window for each patient.

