**Phase 2 – Baseline Characterization**

The baseline characterization will provide the initial clinical evaluation. Upon enrollment, randomization, and patient background collection, an venous blood gas sample will be drawn to establish the patient baseline at the time just prior to placing the patient on either of the study arm therapies (HVNI or NIPPV). Patient baseline for physiologic parameters (RR, HR, SpO2, BP, RPD) and venous blood gas parameters (PCO2, PO2, pH, bicarbonate, base excess,) will be collected at this time, prior to the initiation of the assigned/randomized therapy. A basic metabolic panel (BUN, CO2, Creatinine, Glucose, Chloride, Potassium, Sodium, Calcium) will also be collected at this time. For the RPD, the clinician will record patient scores. Patient Stability Index evaluation will be evaluated by clinicians and recorded at this time, described as follows: to assess patient clinical stability using a continuous VAS score on a scale from unable to speak, due to severe respiratory distress, up to speaks in full sentences without severe respiratory distress.

At baseline, only patient perception scores will take place. During the noted study phases, the clinician and the patient will complete VAS perception scores (annotated on 100mm line with an "X") for their randomized study arm (HVNI or NIPPV). Patient & Clinician Perception Assessment will be performed by the clinician or therapist performing or participating in the testing procedures. The Perception Assessments will be completed for each of the three endpoints for clinician assessment and the two endpoints for the patient assessment. For the patient perception/satisfaction these include: (1) relief of symptoms, and (2) comfort/tolerance. For the clinician perceptions these include: (1) expected/perceived patient outcomes, (2) patient comfort & tolerance, and (3) ease of use.

The assigned therapy per randomization will be implemented per the initial settings identified below, after which settings will be titrated per standard practice for optimal effect. Patients will be managed by routine care while study data is captured as per the timeline given in Table 1. Note: All decision making for intubation, treatment regimen, discharge, and disposition will be made per standard practice at each center using the judgment of the PI, Sub-I or their designee.

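### Neither the intention-to-treat nor the per-protocol set is defined or named as decisive, and incomplete data can remove a randomised patient, so the plan permits a completer analysis of the 4-hour Borg under the intention-to-treat name

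*Combined protocol and SAP*

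**What the plan says.** **Analysis sets.** Section VIII (Statistical Analysis) has one sentence on this, saying that the analysis will be both per protocol and intention-to-treat. No section defines either set, ranks them or requires them to agree. The methods named are a Wilcoxon test by default, a t-test if the data look normal, and repeated-measures ANOVA. No section gives a missing-data method.

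**Who may be left out.** Section VI (Screening, Enrollment, & Management) states: "All patients randomized, but not included in the final study population, will be accounted for in a CONSORT diagram". For the reasons behind such omissions, the same sentence speaks of "noting the dropout criteria (i.e. refused consent, met exclusion criteria, incomplete dataset, etc". The list is open-ended, and neither the final study population nor an incomplete dataset is defined. Section IV adds: "Patients may be excluded after randomization, as this study takes place in the ED or inpatient critical care unit". The reason given there is that patients may have to be randomised and treated at once.

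**Sizing.** Section V bases power on this: "A total sample size of 64 subjects (~32 per arm) randomized with endpoint data". About 80 are to be enrolled, because "there is an expected patient dropout (i.e. incomplete or unusable subject number" is foreseen.

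**Endpoint and early exits.** The hypotheses in Section II concern the "improvement in modified BORG at 4 hours for treatment (Vapotherm) and control (NIPPV" arms). Phases 3 to 5 collect physiologic parameters at intubation or early ED discharge, and Section VII lists rated perceived dyspnea (the Borg) among those parameters. Section V has procedures continue after a transfer within the hospital. No rule says whether an early-exit Borg stands in for the 4-hour value.

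**Deviations.** Section XII counts unfinished phases and inability to complete the assigned arm as deviations, but ties neither to the per-protocol set.

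**The concern.** Standard tests run on this plan would use only patients with an observed 4-hour Borg, and nothing in the text prevents that result from being labelled ITT. The trial is unblinded and the outcome is patient-reported. The treatment-failure definitions in Section VI include device intolerance and failure to ventilate. Loss can therefore plausibly depend on both arm and outcome.

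If HVNI loses more patients with poor relief, a completer test is tilted toward claiming non-inferiority. If NIPPV does, the test is tilted against HVNI. With the deciding set and the handling of missing values both open, the primary conclusion could turn on a choice made after unblinded data have been seen.

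**Working it through.** **1. The plan's own figure.** Inputs from Section V: difference 0.9 favouring HVNI, SDs 2.4 and 2.9, margin 1.0, one-sided alpha 0.025, power 80%.
- Root-mean-square SD = √((2.4² + 2.9²)/2) = 2.662.
- n per arm = 2 × 2.662² × (1.960 + 0.842)² / (1.0 + 0.9)² = 30.8, so 31 by normal approximation.
- By noncentral t, power is 79.0% at 31 per arm and 80.3% at 32.
- 64/0.8 = 80.

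The sample size is right on its own inputs. It is a calculation for 64 completers, with up to 16 of 80 randomised patients (20%) absent.

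**2. Bias from dropping patients.** Let pT and pC be the loss fractions for HVNI and NIPPV, and let lost patients improve d points less than completers in both arms. Each arm's all-randomised mean is its completer mean minus p × d, so

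completer difference = true difference + (pT − pC) × d.

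**3. Type I error of a completer-only test.** Welch t-test, 40 randomised per arm, true difference −1.0, SDs from the Section V table (HVNI 2.931, NIPPV 2.431). The loss splits and d are assumptions.

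| HVNI/NIPPV lost | d = 1 | d = 2 | d = 3 | d = 4 |
|---|---|---|---|---|
| 8/8 | 2.5% | 2.5% | 2.5% | 2.5% |
| 9/7 | 3.0% | 3.5% | 4.1% | 4.8% |
| 10/6 | 3.5% | 4.7% | 6.4% | 8.4% |
| 12/4 | 4.7% | 8.3% | 13.5% | 20.7% |
| 4/12 | 1.2% | 0.5% | 0.2% | 0.1% |

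Example, 12/4 with d = 4: bias = (0.30 − 0.10) × 4 = 0.8; SE = √(2.931²/28 + 2.431²/36) = 0.686; noncentrality = 0.8/0.686 = 1.17; rejection probability 20.7%. Section V's sentence gives the two SDs to the opposite arms from its table. Using the sentence's assignment moves these rates by at most 1.3 points.

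At the table's own difference (4.143 − 3.208 = 0.935), power is 80.7% at 8/8 and falls to between 72.1% (d = 1) and 38.4% (d = 4) at 4/12.

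**4. Half the loss unrelated to outcome.** Take 4 unrelated losses per arm, with the rest split 6/2. If the unrelated losses resemble completers, the bias is (6 − 2)/40 × d = 0.100d, and type I error is 3.5% to 8.4%. If they are a random sample of the arm, the bias is (6 − 2)/36 × d = 0.111d, and type I error is 3.6% to 9.4%.

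**5. Lost patients are failures scored as no improvement.** Take a NIPPV mean of 3.2, an HVNI mean of 2.2 and SD 2.65. Each completer mean is the overall mean divided by (1 − failure rate).

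| HVNI/NIPPV failure | Completer difference | Type I error |
|---|---|---|
| 10%/5% | 2.444 − 3.368 = −0.924 | 3.2% to 3.3% |
| 20%/10% | 2.750 − 3.556 = −0.806 | 4.0% to 4.8% |
| 20%/5% | 2.750 − 3.368 = −0.618 | 7.5% to 8.6% |
| 10%/10% | 2.444 − 3.556 = −1.111 | 1.6% to 1.7% |
| 20%/20% | 2.750 − 4.000 = −1.250 | 1.0% |

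The ranges reflect calculation details, such as whether 3.2 is the mean of all NIPPV patients or of completers. The last two rows show that equal loss and equal outcomes among the lost do not make the bias nil. The gap to completers must match as well.

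**6. Would imputation help?** Simulation, 4,000 to 5,000 trials per cell, 20 imputations within arm from the 30-minute and 1-hour change, assumed 1-hour to 4-hour correlation 0.5 or 0.7, loss about 30%/10%.
- Loss driven by the 1-hour Borg: completers 6.0% to 12.6%, imputation 2.4% to 2.9%.
- Loss driven by the unseen 4-hour value: completers 12.2% to 23.4%, imputation 6.0% to 15.4%. Imputation alone does not suffice here, hence the tipping-point analysis.

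**The case against.** The sentence listing dropout reasons is about CONSORT reporting and is not an analysis rule. Section VIII does commit to ITT, which ordinarily means all randomised patients as assigned. An incomplete dataset could be meant for the per-protocol set only. Section IV's reason for later exclusions, the need to treat at once, reads most naturally as late consent or eligibility findings. Procedures continue after transfer, Borg values are collected at intubation and early discharge, and a repeated-measures analysis could be fitted as a mixed model that uses partial data.

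Much of this stands. A reader might infer that the plan orders a completer analysis, and the text does not support that. What remains is that nothing limits the exclusions to consent or eligibility, CONSORT accounting does not return patients to the analysis, early-exit values have no assigned use, and no mixed model is specified.

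The objection to size also stands in part. A reader might take 20.7% as the expected error rate. It needs the full 20% allowance, a 3:1 split and every lost patient 4 points worse, yet some listed reasons, such as refused consent, need not depend on outcome. The figures are also for a t-test, whereas the plan defaults to a Wilcoxon test.

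**Conclusion.** The concern holds as a gap in definition that must be closed before data are seen: the plan permits a completer analysis under the ITT name. It rests on the text alone, since Figure 1 was not available. The sample-size arithmetic is not at fault.

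Neither the direction nor the size of any bias is established, because the documents give no loss split and no outcomes for lost patients. Under the stated assumptions, moderate imbalance puts one-sided type I error at roughly 3% to 9% against a nominal 2.5%, with 20.7% near the worst case. Heavier NIPPV loss puts it below nominal and costs power. A reader might infer that the plan favours HVNI, and the documents do not show that. The severity rests on the missing definitions and the stated exclusion reason, not on the largest figure.

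**What to change.** - **ITT set.** Define it as all randomised patients in their assigned arm, and remove an incomplete dataset as a reason for exclusion from it. Limit exclusions to two groups. The first is patients whose consent was never validly obtained or who withdraw permission to use their data. The second is patients shown to be ineligible by data from before therapy, judged without knowledge of arm; the baseline blood gas is one such source, as it "will be drawn to establish the patient baseline at the time just prior to placing the patient on either of the study arm therapies". Patients who stop or withdraw after therapy starts stay in, with data up to that point. Report all exclusions by arm.
- **Missing values.** Analyse the 4-hour Borg change with a mixed model or multiple imputation using the baseline, 30-minute and 1-hour Borg, plus a tipping-point analysis.
- **Early exits and switches.** State in advance how a Borg taken at intubation, at early discharge or after a switch of modality enters the primary analysis. Section IV already provides the data: "All respiratory interventions will be tracked during the study window for each patient". The strategy is the sponsor's choice, with one sensitivity analysis that scores failures unfavourably.
- **Decision rule.** Define the per-protocol set. State that non-inferiority is decided by the lower confidence limit exceeding −1.0 in the ITT set, with per-protocol as a pre-specified supporting analysis.
- **Power.** Restate it on that basis.

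The cost is wording and analysis work, since the Borg is already scheduled at all four times. Stated power may fall slightly. With 20% loss per arm, imputation gives 78.3% and 82.8% at correlations 0.5 and 0.7, against 82.4% and 84.6% for completers under the same assumptions. Scoring 20% per arm as no improvement gives 78.3%, against 80.3% if they are dropped.
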